### **3.7.3.5.1      Simpson Angus Scale**

The SAS ([Appendix 9](#)) consists of a list of 10 symptoms of Parkinsonism (gait, arm dropping, shoulder shaking, elbow rigidity, wrist rigidity, head rotation, glabella tap, tremor, salivation, and akathisia). Each item will be rated on a 5-point scale, with a score of zero representing absence of symptoms, and a score of 4 representing a severe condition. The SAS Total Score is the sum of the scores for all 10 items.

Anticholinergics, propranolol, benzodiazepines, and non-benzodiazepine sleep aids are not permitted within 12 hours of scale administration (see [Section 4](#)). Investigators are encouraged to delay scale administration until 12 hours have elapsed, if at all possible. However, if delaying administration of the scale is not feasible, the SAS should still be administered and the use of the medication documented, including a notation of the drug name, dose, and time of administration on the eSource.

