### **3.7.3.5.2      Abnormal Involuntary Movement Scale**

The AIMS assessment ([Appendix 10](#)) consists of 10 items describing symptoms of dyskinesia. Facial and oral movements (items 1 through 4), extremity movements (items 5 and 6), and trunk movements (item 7) will be observed unobtrusively while the subject is at rest (eg, in the waiting room), and the investigator will also make global judgments on the subject's dyskinesias (items 8 through 10). Each item will be rated on a 5-point scale, with a score of zero representing absence of symptoms (for item 10, no awareness), and a score of 4 indicating a severe condition (for item 10, awareness, severe distress). For this scale, the subject is to be sitting on a hard, firm chair. In addition, the AIMS includes two yes/no questions that address the subject's dental status. Anticholinergics, propranolol, benzodiazepines, and non-benzodiazepine sleep aids are not permitted within 12 hours of scale administration (see [Section 4](#)). Investigators are encouraged to delay scale administration until 12 hours have elapsed, if at all possible. However, if delaying administration of the scale is not feasible, the AIMS should still be administered and the use of the medication documented, including a notation of the drug name, dose, and time of administration on the eSource.

The AIMS Movement Rating Score is defined as the sum of items 1 through 7 (ie, items 1 through 4, facial and oral movements; items 5 and 6, extremity movements; and item 7, trunk movements).

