### **3.7.3.5.3 Barnes Akathisia Rating Scale**

The BARS ([Appendix 11](#)) consists of 4 items related to akathisia: objective observation of akathisia by the investigator, subjective feelings of restlessness by the subject, subjective distress due to akathisia, and global clinical assessment of akathisia. The first 3 items will be rated on a 4-point scale, with a score of zero representing absence of symptoms and a score of 3 representing a severe condition. The global clinical evaluation will be made on a 6-point scale, with zero representing absence of symptoms and a score of 5 representing severe akathisia. To complete this scale, subjects will be observed while they are seated and then standing for a minimum of 2 minutes in each position. Symptoms observed in other situations (eg, while engaged in neutral conversation or engaged in activity on the ward) may also be rated. Subjective phenomena are to be elicited by direct questioning. Anticholinergics, propranolol, benzodiazepines, and non-benzodiazepine sleep aids are not permitted within 12 hours of scale administration (see [Section 4](#)). Investigators are encouraged to delay scale administration until 12 hours have elapsed, if at all possible. However, if delaying administration of the scale is not feasible, the BARS should still be administered and the use of the medication documented, including a notation of the drug name, dose, and time of administration on the eSource.

The BARS Global Score is defined as the global clinical assessment of akathisia.

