## 4.2 Other Restrictions

### 4.2.1 Restricted Therapies and Precautions

Any history of electroconvulsive therapy is exclusionary.

Use of intramuscular (IM) benzodiazepines is prohibited throughout the trial. Short-term use of specific oral benzodiazepines is allowed during the trial for the control of agitation or insomnia as shown in [Table 4.1-3](#). Short-acting benzodiazepines (ie, lorazepam or oxazepam) are to be used whenever possible. In countries or institutions where no short-acting benzodiazepines are commercially available, use of oral diazepam or oral clonazepam may be acceptable if prior authorization is obtained from the medical monitor. The investigator should contact the medical monitor to discuss any subject who requires frequent use of a benzodiazepine for agitation or insomnia beyond the first 2 weeks of the trial.

Non-benzodiazepine sleep aids (ie, zolpidem, zaleplon, zopiclone, and eszopiclone only) are permitted for the treatment of insomnia, but not on the same day as administration of a benzodiazepine, regardless of indication. For the non-benzodiazepine sleep aids, sites should only utilize 1 of the listed medications that are approved for this indication in their respective countries and the country-specific prescribing information is to be used to determine the maximum allowable daily dose for the treatment of insomnia.

Anticholinergics are permitted for the treatment of EPS up to a maximum of 4 mg/day benztrapine or its equivalent and propranolol is permitted for akathisia or tremor up to a maximum of 60 mg/day. Subjects receiving a stable dose of propranolol for other conditions at entry into Trial 331-10-236 may remain on propranolol. Trial sites should only utilize medications that are approved for these indications in their respective countries.

Benzodiazepines, non-benzodiazepine sleep aids, anticholinergics, and propranolol must not be administered within 12 hours prior to scheduled efficacy and safety assessments, including EPS scales. Investigators are encouraged to delay scale administration until 12 hours have elapsed, if at all possible. However, if delaying administration of efficacy and safety scales is not feasible, the scales should still be administered and the use of the medication documented, including a notation of the drug name, dose, and time of administration on the eSource.

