8.2.6.2 Extrapiramidal Symptoms

A data summary will be provided for the 24-month open-label treatment period only, since there are no assessments of the EPS scales in the conversion period.

Three EPS scales including the SAS, AIMS, and BARS will be assessed at the baseline visit and the following visits in the 24-month open-label treatment period: Weeks 1, 2, and 4; Months 2, 3, 4, 6, 8, 10, 12, 15, 18, and 24; or an ET visit. Change from baseline in each of the 3 EPS variables (SAS total score, AIMS total score, and BARS global clinical assessment score) will be summarized on the OC data by visit and on the LOCF data for the last assessment visit. In addition, the BARS global clinical assessment will be treated as a categorical variable taking values (categories) of “Absent”, “Questionable”,

“Mild Akathisia”, “Marked Akathisia”, and “Severe Akathisia”, and thus will be summarized on OC data by visit for each severity category, by using count and frequency.

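### EPS ratings made within 12 hours of a restricted drug are recorded as such, but SAP 8.2.6.2 pools them unmarked, so possible masking of SAS and BARS scores cannot be seen

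*SAP*

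**What the plan says.** **Protocol.** Section 3.7.3.5.1 (SAS) sets the rule: "Anticholinergics, propranolol, benzodiazepines, and non-benzodiazepine sleep aids are not permitted within 12 hours of scale administration". Sections 3.7.3.5.2 (AIMS) and 3.7.3.5.3 (BARS) repeat it, and 4.2.1 widens it: "Benzodiazepines, non-benzodiazepine sleep aids, anticholinergics, and propranolol must not be administered within 12 hours prior to scheduled efficacy and safety assessments". There is an exception. If the rating cannot reasonably be put off, "the SAS should still be administered and the use of the medication documented". The other two scales have the same exception: "the AIMS should still be administered and the use of the medication documented" and "the BARS should still be administered and the use of the medication documented". In each case the drug, its dose and when it was taken go into eSource.

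Section 4.2.1 also says why two of these drug classes may be in use: "Anticholinergics are permitted for the treatment of EPS", and "propranolol is permitted for akathisia or tremor".

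**SAP.** Section 8.2.6.2 summarizes change from baseline in three variables ("SAS total score, AIMS total score, and BARS global clinical assessment score) will be summarized on the OC data by visit") and again, by LOCF, at the last assessment visit. It also counts subjects in each BARS global severity category at each visit. It does not mention ratings made inside the 12-hour window.

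**The concern.** The protocol takes the trouble to record when a rating falls inside the window, and the analysis plan then ignores the record. SAS rates rigidity, tremor and akathisia among its ten items, and BARS rates akathisia. A score obtained shortly after an anticholinergic given for EPS, or propranolol given for akathisia or tremor, describes treated signs in a subject who needed treatment.

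Mean change on these scales is a secondary safety endpoint (Protocol 3.5.2.1). The trial is single-arm (SAP 3), so no concurrent control group would show the same masking. A reader who sees a flat EPS trend over 24 months cannot tell whether EPS was absent or was being medicated when rated.

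**Working it through.** **1. Is the record used anywhere in the SAP?**

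| SAP section | What it does with these ratings |
|---|---|
| 8.2.6.2 | All observed ratings by visit, plus LOCF; no flag, exclusion or sensitivity analysis |
| 8.2.7 | Rules for missing items only |
| 10.2 | If several ratings fall in one window, the last is used, so a rating under medication can displace a clean one |
| 10.5 | Such a rating can also supply the last-visit value |
| 8.1 | EPS-related TEAEs, a separate outcome |
| 8.3 | Concomitant drugs by class and generic name for whole periods, not by visit or rating time |
| 6.3 | Deviations, including those on concomitant medication, not linked to scores |

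The record is not used, and no other table shows which scores are affected.

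**2. Where do the documents support masking?** Protocol 4.2.1 ties anticholinergics to EPS and propranolol to akathisia or tremor. That supports possible masking of SAS and BARS by these two. The documents show no direction for AIMS, or for benzodiazepines and sleep aids on any of the scales. Those belong in the flag because the 12-hour rule covers them, not because an effect is shown.

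**3. Mean change from baseline.** The plan has no figure to reproduce: the sample size is not based on power, and no EPS effect or SD is given. The inputs below are therefore assumptions: share of ratings affected after baseline p1 = 2% to 20%, share affected at baseline p0 = 0% to 10%, and points masked per affected rating m = 0.5 to 3, taken as equal at both times.

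Bias in mean change = -(p1 - p0) x m

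| p0 | p1 | m | Bias (points) |
|---|---|---|---|
| 0% | 2% | 0.5 | -(0.02) x 0.5 = -0.01 |
| 0% | 5% | 1 | -(0.05) x 1 = -0.05 |
| 0% | 10% | 2 | -(0.10) x 2 = -0.20 |
| 0% | 20% | 3 | -(0.20) x 3 = -0.60 |
| 10% | 10% | any | 0 |
| 10% | 5% | 1 | +(0.05) x 1 = +0.05 |
| 10% | 5% | 3 | +(0.05) x 3 = +0.15 |
| 10% | 2% | 3 | +(0.08) x 3 = +0.24 |

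The sign depends on whether more ratings are affected after baseline or at baseline, which the documents do not tell us.

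**4. BARS severity categories.** These are levels at each visit, not changes, so masking at baseline cannot offset masking later. Masked ratings move subjects only toward milder rows. The share moved at a visit is at most p1, and reaches p1 only if every affected rating is masked enough to change category.

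**5. Would dropping the affected ratings repair it?** Let affected subjects truly score d points higher than the rest, and let p be their share.

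- Pooling biases the mean level by -p x m.
- Exclusion biases it by -p x d.

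With p = 10%, d = 3 and m = 1, pooling gives -0.1 and exclusion -0.3. With p = 10%, d = 1 and m = 2, pooling gives -0.2 and exclusion -0.1. Exclusion can be better or worse than pooling, because it removes treated subjects.

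**The case against.** The protocol does not call such ratings invalid. It bars the drugs, encourages delay, and then says to rate anyway, so including these scores in an observed-case summary is consistent with it. It also tries to keep them few, and a share near zero is plausible. Even the extreme of 0.60 points is small on SAS, which runs to 10 x 4 = 40. EPS-related TEAEs are in the primary safety analysis, and overall anticholinergic and propranolol use will appear in the concomitant medication table, so treated EPS is not hidden from the report. A 12-hour flag also misses a subject treated daily but rated 13 hours after a dose. The trial is descriptive throughout.

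Most of this stands. It is a reason to keep all ratings in the main summaries and not to rely on the flag alone. It does not answer the omission: none of these tables says how many scores at a visit were obtained under a restricted drug.

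A reader might go further and infer that the SAS, AIMS and BARS means understate EPS, always in one direction and increasingly over time. The documents do not support that. The SAP summarizes change, and baseline may be affected as well. For rollover subjects, baseline is the parent trial's Week 6 rating; for de novo subjects it is generally the last value before open-label dosing (SAP 7.1.1). Limited oral benzodiazepine use is allowed during screening (Protocol Table 4.1-1), and subjects on stable propranolol for another condition may stay on it (4.2.1). Growth over time is conjecture, since no document gives the pattern of use.

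**Conclusion.** The point holds as an unhandled data feature, not as a demonstrated bias toward fewer EPS. The SAP pools ratings made inside the protocol's 12-hour window with the others and never uses the information collected about them. SAS and BARS scores rated under an anticholinergic or propranolol can be masked, and BARS severity counts by visit can be shifted toward milder categories.

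For mean change from baseline, size and direction are unknown. The illustrative range of -0.60 to +0.24 points rests wholly on assumed shares and assumed masking. The negative extreme further assumes that no baseline rating is affected, and the positive extreme that 10% are. No direction can be claimed for AIMS.

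This is a cheap improvement to a secondary safety analysis. It does not call the primary safety outcomes into question.

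**What to change.** In SAP 8.2.6.2:

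1. Keep all ratings in the main by-visit, last-visit and BARS category summaries.
2. Flag each SAS, AIMS and BARS rating made within 12 hours of a listed drug, using the time in eSource, and report the number and percent flagged at baseline and at each visit.
3. Repeat the three sets of summaries without flagged ratings as a sensitivity analysis only, with a note that exclusion removes treated subjects and can itself lower the means.
4. Tabulate by visit the percent of subjects with a worsened score, or with an anticholinergic or propranolol started after baseline. Define worsening in advance. This row also catches treated subjects whose rating fell outside the 12 hours. It should rest on drug starts after baseline, because the entries required for the 12-hour exception cover drug, dose and time but not the reason for use. A start for some other reason would therefore be counted too.

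The cost is SAP wording, one derived flag and a few more table rows, from data the protocol already requires. Trial conduct does not change. The sensitivity tables will rest on fewer ratings. Settling this before database lock avoids a choice made after seeing the scores.

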8.2.6.3 Suicidality

Suicidality will be monitored during the trial (including the 1- to 4-week conversion period but excluding the 21-day follow-up period) by using the C-SSRS. A data summary will be provided separately for the open-label treatment period and for the conversion period.

Suicidality data (including suicidal ideation, suicidal behavior) will be collected at all scheduled visits and the ET visit.

Suicidal ideation has 5 types or levels, with increasing severity from “wish to be dead” to “active suicidal ideation with specific plan and intent”. The incidence of each type of suicidal ideation will be summarized for the reporting period (ie, separately for the open-label period and for the conversion period). Suicidal behavior has several types or levels ranging from “actual attempt”, “interrupted attempt”, “aborted attempt” to “completed suicide”. The incidence of each type of suicidal behavior will be summarized for the reporting period.

Additionally, the incidence of each of the following 4 categories of treatment-emergent suicidality will be summarized for the reporting period: (1) Emergence of suicidal ideation, which is defined as having an occurrence of any suicidal ideation during the reporting period while having no suicidal ideation at the baseline (relative to the reporting period); (2) Emergence of serious suicidal ideation, which is defined as having an observation of suicidal ideation severity rating of 4 or 5 during the reporting period while having no suicidal ideation at the baseline (relative to the reporting period); (3) Worsening of suicidal ideation, which is defined as having had a suicidal ideation severity rating that is more severe compared to the baseline (relative to the reporting period); and (4) Emergence of suicidal behavior, which is defined as reporting of any suicidal behavior during the reporting period while there was no suicidal behavior at the baseline (relative to the reporting period). Specifically, for each category of treatment-emergent suicidality as defined above, the number and percentage of subjects having experienced the event of interest during the reporting period will be tabulated.

8.2.6.4 Tanner Stage

A data summary will be provided for the 24-month open-label treatment period only. There are no ratings of the Tanner Staging (a classification of sexual maturity stages) in the conversion period.

The Tanner Staging scores are collected at baseline and at the following scheduled visits in the 24-month open-label treatment period: Months 6, 12, 18, and 24. The shifting frequency in Tanner Staging score (an ordinal score of 1 to 5) between baseline and each postbaseline visit will be tabulated separately for boys and girls by using cross-frequency. If the subject is rated “5” at a visit before Month 24 and is not rated thereafter, missing ratings at the subject’s subsequent visits will be imputed with the value of “5”.

8.2.7 Computational Details for Safety Scales

- 1) The SAS total score is the sum of rating scores over 10 items from the SAS panel in the eSource. The SAS total score is treated as unevaluable if fewer than 8 of the 10 items are recorded. If 8 or 9 of the 10 items are recorded, the SAS total score will be calculated as the mean of the recorded items multiplied by 10 and then rounded to the first decimal place.
- 2) The AIMS movement total score is the sum of rating scores for facial and oral movements (ie, items 1 - 4), extremity movements (ie, items 5 - 6), and trunk movements (ie, item 7). The AIMS total score will be treated as unevaluable if fewer than 6 of the 7 items are recorded. If 6 of the 7 items are recorded, the total score will be calculated as the mean of the recorded items multiplied by 7 and then rounded to the first decimal place.
- 3) The BARS score is based only on the item of “Global Clinical Assessment of Akathisia”. The BARS consists of 4 items related to akathisia as follows. Item 1: objective observation of akathisia by the investigator; Item 2: subjective feelings of restlessness by the subject; Item 3: subjective distress due to akathisia; and Item 4: global clinical assessment of akathisia. The first 3 items will be rated on a 4-point Likert scale from 0 to 3, with 0 representing the absence of symptoms and 3 representing a severe condition. The BARS global clinical assessment score refers to the ratings from the fourth item Global Clinical Assessment of Akathisia, which is a 6-point Likert scale from 0 to 5, with 0 representing absence of symptoms and 5 representing severe akathisia. Thus, the BARS global clinical assessment score ranges from 0 to 5.
- 4) The NY-AACENT is intended to be used to detect changes in cognitive function subsequent to pharmacological or similar treatments for neurological or psychiatric problems. It is specifically designed to be used in pediatric populations (ages 12 to 17), though can be utilized with other age groups as appropriate. Each of the 7 items are derived from the 7 domains as follows: Working Memory, Attention/Vigilance, Verbal Learning/Memory, Visual Learning/Memory, Reasoning and Problem Solving, Speed of Processing, and Social Cognition. Each item score is derived as follows: 0 = not present in the past week; 1 = present (during past week) and mild; 2 = present (during past week) and moderate; 3 = present (during past week) and severe; and 4 = present (during past week) and extreme; and the item score is set to missing/unknown if otherwise. The NY-AACENT total score is calculated by summing up the 7 individual item scores at the subject-visit level. If 3 or more than 3 individual item scores are missing/unknown, the NY-AACENT total score cannot be calculated and will be

set to missing; if 1 or 2 individual item scores are missing/unknown, the NY-AACENT total score equals the average score of the non-missing items multiplied by 7 and then rounded to the first decimal place.

- 5) Each item (ie, each symptom) of the UKU Side Effects Rating Scale is defined by the means of a 4-point-scale (0-1-2-3) if it is assessed. In general, Degree 0 means "not or doubtfully present", and Degrees 1, 2, and 3 indicate that the symptom is present to a mild, moderate, or severe degree, respectively.

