### **7.5.5 Other Safety Data**

#### **7.5.5.1 Special Pediatric Safety Assessments**

Some special pediatric safety assessments will be performed in this trial. They include comprehensive psychotropic side effects as assessed by the UKU side effect rating scale, and cognitive adverse effects as assessed by NY-AACENT.

Descriptive statistics will be provided for the frequency of symptom items recorded in the Safety Sample. In addition, for symptoms recorded in NY-AACENT, a total score at any level of present, attribution, severity or impairment may be calculated. The total score and its change from baseline at each visit will be summarized using descriptive statistics for the Safety Sample by disease under study.

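### The NY-AACENT scoring rule treats a symptom recorded as present but not graded as missing, so the total score can fall below the lowest value the record permits

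*SAP*

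**What the plan says.** SAP 8.2.7 item 4 builds each of the seven item scores from two facts: whether the symptom was present in the past week and how severe it was. The bottom of the scale is "0 = not present in the past week". The next step is "1 = present (during past week) and mild", and 2, 3 and 4 likewise need presence together with a grade of moderate, severe or extreme. Every other combination falls into the residual clause: "and the item score is set to missing/unknown if otherwise".

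The total follows: "The NY-AACENT total score is calculated by summing up the 7 individual item scores at the subject-visit level". There are two rules for incomplete records. "If 3 or more than 3 individual item scores are missing/unknown, the NY-AACENT total score cannot be calculated"; and "if 1 or 2 individual item scores are missing/unknown, the NY-AACENT total score equals the average score of the non-missing items multiplied by 7", rounded to one decimal.

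Protocol 7.5.5.1 treats presence and severity as distinct levels of the record, since "a total score at any level of present, attribution, severity or impairment may be calculated". SAP 8.2.6.1 tabulates the incidence and severity of individual items by visit, repeats this for drug-related and for function-impaired items, and then adds change from baseline in the total, on observed cases by visit and on LOCF data at the last visit.

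**The concern.** A symptom marked present with no grade is only partly unknown. On the SAP's own scale its score is at least 1. The residual clause discards that knowledge, and proration then fills the gap with the average of the other items. When most of those are absent, the average is below 1.

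Proration elsewhere in the SAP does not have this problem. The SAS and AIMS rules (SAP 8.2.7 items 1 and 2) and the PANSS rules (SAP 9.4) work on single ratings that are either recorded or not, so no known information is thrown away. The NY-AACENT item score combines two pieces of information, and one can be known without the other.

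At stake is the correctness of individual totals and their changes from baseline in a long-term safety trial in adolescents. A total of 0.0 could appear for a subject whose item record shows a cognitive symptom at the same visit.

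**Working it through.** **Inputs, all from SAP 8.2.7 item 4.** Seven items; absent = 0; present and graded = 1, 2, 3 or 4; anything else is missing. With k missing items and a sum S over the 7 − k scored items:

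- k = 0, 1 or 2: total = S / (7 − k) × 7, to one decimal
- k ≥ 3: total missing

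The plan states no figure to reproduce here, so the rule is applied directly.

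**Permitted range.** If all k missing items are present but ungraded, each is worth 1 to 4, so the record permits totals from S + k to S + 4k.

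| Record | SAP total | Permitted by the record |
|---|---|---|
| 7 absent | 0/7 × 7 = 0.0 | 0 |
| 1 ungraded, 6 absent | 0/6 × 7 = 0.0 | 1 to 4 |
| 2 ungraded, 5 absent | 0/5 × 7 = 0.0 | 2 to 8 |
| 1 ungraded, 1 mild, 5 absent | 1/6 × 7 = 1.2 | 2 to 5 |
| 1 ungraded, 1 moderate, 5 absent | 2/6 × 7 = 2.3 | 3 to 6 |
| 2 ungraded, 1 mild, 4 absent | 1/5 × 7 = 1.4 | 3 to 9 |
| 1 ungraded, 6 mild | 6/6 × 7 = 7.0 | 7 to 10 |
| 1 ungraded, 6 extreme | 24/6 × 7 = 28.0 | 25 to 28 |
| 3 ungraded, 4 absent | missing | 3 to 12 |

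**When the total is infeasible.** Proration gives each ungraded item the value S / (7 − k). That never exceeds 4, so the total cannot exceed the upper limit. It falls below the lower limit exactly when S / (7 − k) < 1: S below 6 with one ungraded item, or below 5 with two. A total of exactly 0.0 needs every other item to be absent.

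**Change from baseline, other items absent.**

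- One mild item at baseline, the same item present but ungraded later: 0.0 − 1.0 = −1.0. The record permits 1 − 1 = 0 to 4 − 1 = +3, so a persisting symptom appears as an improvement.
- The item ungraded at baseline, mild later: 1.0 − 0.0 = +1.0. The record permits 1 − 4 = −3 to 1 − 1 = 0, so a worsening appears that the record rules out.

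**Effect on a visit mean.** The documents give no frequency for the pattern. Assume, for illustration only, that 1% to 5% of subject-visits have one ungraded item with all others absent. The understatement of the visit mean is then 1% × 1 = 0.01 to 5% × 4 = 0.20 points, on a scale from 0 to 7 × 4 = 28.

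**The case against.** The strongest reply is that the pattern may never occur. The NY-AACENT form (protocol Appendix 13) is not in the available text, and protocol 9.2 describes direct capture in a validated electronic system whose edit checks are not described. Separate levels for presence and severity do not prove that one can be saved without the other. This stands: the fault is in the written rule, and its frequency is unknown.

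Second, a reader might infer that the total is the trial's main measure of cognitive harm. The documents do not support that. The secondary endpoint in protocol 3.5.2.1 is the frequency of symptom items. Protocol 7.5.5.1 makes the total optional, and SAP 8.2.6.1 adds it after the item tables. Nothing there removes an ungraded item from the incidence count, although the SAP does not say how one is counted; SAP 10.6 provides for a missing or unknown row in categorical tables. The summaries are descriptive, and protocol 3.7.3.5.5 says the scale is not validated.

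Third, a reader might infer a consistent bias towards finding no cognitive harm. That also fails. An ungraded item at baseline can create a false worsening, and with six extreme items the prorated total sits at the top of the permitted range.

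Fourth, proration is the SAP's general convention, and always scoring such items 1 has its own cost. With six severe items and one ungraded, proration gives 18/6 × 7 = 21.0 and a flat 1 gives 18 + 1 = 19, in a permitted range of 19 to 22. This bears on the choice of remedy. It does not defend a total below the permitted range.

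**Conclusion.** The point holds as a flaw in a derivation rule. As written, the rule produces totals that contradict the record whenever one or two items are present but ungraded and the scored items average below 1. In the sparse-symptom cases worked above, the shortfall against the lowest permitted total is 0.7 to 2 points: 3 − 2.3 = 0.7 at the smallest and 2 − 0.0 = 2 at the largest. With three or more such items, a subject with at least three recorded symptoms has no total at that visit.

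The consequence is small. It is confined to a supportive descriptive score and its change from baseline, no inferential analysis depends on it, and under the illustrative frequencies the visit mean moves by at most 0.20 points. The conclusion assumes that eSource can hold presence without severity; if it cannot, the rule does no harm. Two stronger readings, that the cognitive secondary endpoint is compromised and that the error systematically hides harm, are not supported.

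**What to change.** In SAP 8.2.7 item 4, stop counting an item recorded as present with severity unknown as missing. Score it as the larger of 1 and the mean of the scored items (1 if no item has a score). Reserve missing status, the proration and the three-item rule for items whose presence is unknown.

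This keeps the total within the permitted range in the cases checked:

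- 1 ungraded, 6 absent: 0 + 1 = 1
- 2 ungraded, 5 absent: 0 + 2 = 2
- 1 ungraded, 1 moderate, 5 absent: 2 + 1 = 3
- 1 ungraded, 6 severe: 18 + 3 = 21, as under proration
- 3 ungraded, 4 absent: 0 + 3 = 3, where the present rule gives no total

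A simpler alternative is to score such items 1 and state that the total is a lower bound.

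The cost is one extra derivation line. The imputed grade remains approximate: a severe item later recorded as present but ungraded, with the others absent, would show 1 − 3 = −2 instead of 0 − 3 = −3, where the record permits −2 to +1. If eSource forces a grade whenever presence is recorded, the line never takes effect.
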